7.3.2. Treatment Compliance and Modifications

Responses to questions regarding study drug compliance will be collected via a phone questionnaire or web-based application, first weekly for the first 6 months, then monthly. At each assessment, the application collects the number of doses missed for the past week for weekly assessments and past month for monthly assessments. The number of reported missed doses for completed assessments will be used for calculating the compliance of each reporting period. The per participant treatment compliance will be the mean value of the compliance calculated for each reporting period. For each reporting period, compliance will be calculated as (Number of Days in the reporting period – Number of Reported Missed Doses During the reporting period) / Number of Days in the reporting period × 100 as the expected number of doses is once per day. The number of days per dosing period will be 7 for weekly reports, 30 for monthly reports. If the dosing regimen is altered to 3 times/Week dosing for a participant for safety reasons, the denominator will only include planned dosing dates (e.g., 3 doses per week period, 13 doses per month period). The number and percentage of participants in each compliance category (≥ 90 , ≥ 70 to < 90 , ≥ 50 to < 70 , ≥ 30 to < 50 , < 30 , NC) will also be summarized. Compliance will be summarized for overall exposure to any study drug, exposure for each treatment regardless of initial randomized treatment, and exposure to each treatment by initial randomized treatment group using the Safety analysis set. Compliance will be summarized separately for participants who submit a minimum number of questionnaires, with that number determined based on data availability as the study progresses.

8. Efficacy Analysis

The analysis of the primary endpoint will be based on the FAS. The analysis will group participants according to initial randomized treatment regardless of the status of escape medication. As a sensitivity analysis, an analysis will be repeated for the PPS and using other imputation approaches for the FAS.

All secondary endpoints will be primarily analyzed for the FAS and repeated for the Per-Protocol Analysis Set as sensitivity analyses. Sensitivity analyses using other imputation approaches will be performed for the key secondary efficacy endpoints for the FAS. For the EU submission special subgroups will be analyzed for FAS participants.

For all statistical tests, unless otherwise stated, a two-sided type I error rate of 5% will be used, with corresponding 95% CIs and associated p-values provided as appropriate.

All efficacy endpoints will be summarized by treatment group and visit per the reporting conventions described in Section 4. Individual participant listings for each efficacy endpoint will be provided to support the summary tables.

Note: In the event that a site is identified as having significant improper investigator oversight, the primary and secondary efficacy analyses will be performed both with and without this site's data to assess its significance.

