- i. BCVA will be measured in each eye prior to cycloplegia with the participant wearing current correction and will be qualified by study-certified visual acuity testing using the ETDRS charts. If the vision is more than 1 line (≥ 5 letters) worse than baseline, the testing will be redone using trial frames or phoropter. Standard manual refraction may also be performed, if needed, to confirm loss of BCVA using the standard refraction technique.
- j. Corneal endothelial cell count data will be obtained using specular microscopy (selected sites only; approximately 25% of participants).
- k. IOP measurements will be taken prior to pupil dilation.
- l. For cycloplegic autorefraction, 1 drop of 1% cyclopentolate will be applied 2 times to each eye, with 5 minutes between drops. The autorefraction will occur at least 40 minutes (but no more than 60 minutes) after the second drop of 1% cyclopentolate has been instilled. If a participant has progression of myopia >0.75 D, the participant will need to return to the clinic within 3 to 28 days for an unscheduled visit to confirm the progression. Standard manual refraction should be performed at screening for initial BCVA and if Spherical Equivalent is ≥ 0.75 D (to verify components of inclusion #9) and may be performed as needed throughout the study.
- m. Axial length will be measured by cycloplegic biometry (at sites with the requisite equipment; at least 50% of participants).
- n. At Week 2, and between clinic visits, the study coordinator will phone the participant or parent/guardian to encourage compliance and ask about any complaints (potential AEs).
- o. Time spent on various activities (near-vision activities, daylight outdoor leisure, exercise, wearing a wide-brimmed hat or dark glasses while outdoors) and adherence to the dosing regimen will be collected via a questionnaire on a phone or web-based application. The questionnaires will be completed weekly for the first 6 months and then monthly until Month 48/End of Study.

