All study-related raw data that support the corresponding tables and figures will be presented in data listings. Additional data listings may be generated as needed. All table, listing and figure shells will appear in landscape format employing Courier New 9-point font. Unless otherwise noted, all tables will summarize participant results by treatment group sorted in the following order: Vehicle, SYD-101 0.01% and SYD-101 0.03%. After receipt of escape therapy or re-randomization, participants will be summarized under current treatment with the treatment group divided to show initial and current treatment (e.g., Vehicle to Escape, SYD-101 0.01% re-randomized to Vehicle, etc.). Unless otherwise noted, all data listings will be sorted by treatment group and participant identification number defined as investigator identification number concatenated with the participant number. Due to family relocation or site closure, participants could be transferred from one site to a different site. In such cases, participant identification number will remain unchanged. Participants who changed study sites will be included in a data listing.

The baseline value for an assessment is defined as the last non-missing measurement including unscheduled assessments before or on the day of treatment with study drug (Day 1). Change from baseline is defined as the post-baseline value minus the baseline value for the given

assessment. Please also see Section 9 for details regarding baseline considerations for safety analyses when participants receive more than one treatment.

When study day is used for display or in comparisons, the following algorithm will be used:

- study day = date of assessment - date of first dose +1,
if date of assessment \geq first dose date.
- study day = date of assessment - date of first dose,
if date of assessment $<$ first dose date.

Note that the date of first dose is Day 1 and the day before the date of first dose is Day -1 (for analysis, there is no Day 0 for study day). First dose refers to first dose of any study treatment unless otherwise specified.

For all efficacy and safety analyses, analysis visit windows will be used for assigning assessments to an analysis visit, as per [Table 4-1](#) below.

Table 4-1 Visit Windows

Scheduled Visit	Target Day	Analysis Visit Window (Days)
Screening	-21 to 1	Not applicable
Day 1	1	Not applicable
Week 2	14	2 to 52
Month 3	91	53 to 136
Month 6	182	137 to 231
Month 9	280	232 to 322
Month 12	364	323 to 409

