5.2. Protocol Deviations

Protocol deviations will be tracked by the clinical team on an ongoing basis based on the Protocol Deviations Rules document. The Protocol Deviation Rules document includes a description of identified potential deviations and assigns a rule number, deviation type (ICH/GCP Deviation vs. Protocol Deviation), deviation subtype (inclusion/exclusion criteria, visit scheduling, missing doses, treatment compliance, etc.), deviation type (efficacy vs. safety), significance (Significant vs. Non-Significant), deviation source (Medical Monitor Review, Site Monitoring, Automated Data Checks, etc.) and severity (Include Participant in All Analyses, Exclude Participant from PPS, Exclude efficacy assessments after date of deviation, Exclude efficacy assessment on the date of deviation, etc.) for each deviation. The Study Deviations Rules document may be updated as the study is ongoing and new deviations are identified. Each approved version of the Study Deviations Rules document will be maintained in the clinical project files.

Major protocol deviations are defined as the subset of deviations which are considered to have potential significant impact on analysis and results in the exclusion of a participant's data from analysis. Major protocol deviations that may be considered include, but are not limited to the following:

- Failure to fulfill any of the important inclusion/exclusion criteria
- Significant deviations in dosing adherence
- Taking prohibited medication or treatment listed in protocol Section 6.5.1
- Significant deviations in autorefraction process (e.g., only one autorefraction measurement taken per eye)

Participants with major protocol deviations will be tabulated by deviation sub-type for each treatment group. All percentages will be based on the number of FAS participants. Additionally, all major and minor deviations will be listed for all FAS participants.

6. Demographics and Baseline Characteristics

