- n. At Week 2, and between clinic visits, the study coordinator will phone the participant or parent/guardian to encourage compliance and ask about any complaints (potential AEs).
- o. Time spent on various activities (near-vision activities, daylight outdoor leisure, exercise, wearing a wide-brimmed hat or dark glasses while outdoors) and adherence to the dosing regimen will be collected via a questionnaire on a phone or web-based application. The questionnaires will be completed weekly for the first 6 months (through Week 27) and then monthly from Month 7 until Month 48/End of Study.

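### Per-participant compliance averages 7-day and 30-day reports with equal weight, so the first 6 months count for far more than their share of time and the figure is biased whenever adherence changes after Month 6

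*SAP*

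**What the plan says.** SAP 7.3.2 (Treatment Compliance and Modifications) fixes the whole calculation.

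- Frequency of reports: "first weekly for the first 6 months, then monthly". The SAP schedule of events (14.2, footnote o) is slightly more specific: "weekly for the first 6 months (through Week 27) and then monthly from Month 7 until Month 48/End of Study". The protocol schedule (1.3, footnote o) agrees on the switch: "The questionnaires will be completed weekly for the first 6 months and then monthly until Month 48/End of Study".
- Length of a period: "The number of days per dosing period will be 7 for weekly reports, 30 for monthly reports". If dosing is reduced to three times a week for a participant, the denominators become 3 per weekly and 13 per monthly report.
- Which reports count: "The number of reported missed doses for completed assessments will be used for calculating the compliance of each reporting period".
- Summary per participant: "The per participant treatment compliance will be the mean value of the compliance calculated for each reporting period".

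The result is also grouped into categories (at least 90; 70 to below 90; 50 to below 70; 30 to below 50; below 30). It is shown for overall exposure and by treatment, using the Safety set. A separate summary is planned for participants who returned some minimum number of questionnaires. That summary selects participants; it does not change the weights.

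**The concern.** An unweighted mean of period percentages does no harm when the periods are of equal length. Here they differ more than fourfold, so the statistic describes neither the proportion of doses taken nor average adherence over time. The primary endpoints are at Month 24 (EMA) and Month 36 (FDA), and 75% and 83% of those intervals lie after Month 6, in the part that the formula down-weights.

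What is at stake is the accuracy of a reported figure. A reader of the study report will take it as adherence over the treatment period, and some participants will be placed in a category that does not match the doses they reported taking.

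**Working it through.** The documents give no compliance figure or weight to reproduce, so the check is direct arithmetic from the SAP definitions.

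**Inputs.** SAP Table 4-1 puts the Month 6 target at day 182 ("Month 6 182 137 to 231"), and 182/7 = 26 weekly reports. After that there is one report a month: 18 by Month 24, 30 by Month 36 and 42 by Month 48.

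**Weight of one missed dose.** In a weekly report it lowers that period by 1/7 = 14.3 points; in a monthly report by 1/30 = 3.3 points. Every period then counts equally, so the ratio is 30/7 = 4.3. On three-times-weekly dosing it is 13/3 = 4.3.

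**Weight of the first 6 months.** With m monthly reports, the SAP rule gives 26/(26 + m). Weighting by days gives 182/(182 + 30m).

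| Analysis | SAP rule | Day-weighted | Share of time |
|---|---|---|---|
| Month 24 | 26/44 = 59.1% | 182/722 = 25.2% | 6/24 = 25.0% |
| Month 36 | 26/56 = 46.4% | 182/1082 = 16.8% | 6/36 = 16.7% |
| Month 48 | 26/68 = 38.2% | 182/1442 = 12.6% | 6/48 = 12.5% |

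If weekly reports run through Week 27, the Month 24 weight is 27/45 = 60.0%. The Month 48 row applies to overall exposure only: for a treatment first started at Month 36 or at escape, all reports are monthly and no mixing arises.

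**Dependence on completion.** Only completed reports count, and no completion rate is given. The table assumes equal completion in both phases. At Month 24, under assumed uneven completion:

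- all weekly and half of the monthly reports: 26/(26 + 9) = 74.3%
- half of the weekly and all monthly reports: 13/(13 + 18) = 41.9%

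**Effect on the figure at Month 24** (adherence levels are assumptions; all reports completed):

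| Early / later | SAP rule | Dose-weighted |
|---|---|---|
| 95% / 55% | (26×95 + 18×55)/44 = 78.6% | (182×95 + 540×55)/722 = 65.1% |
| 95% / 70% | (26×95 + 18×70)/44 = 84.8% | (182×95 + 540×70)/722 = 76.3% |
| 60% / 100% | (26×60 + 18×100)/44 = 76.4% | (182×60 + 540×100)/722 = 89.9% |
| 90% / 90% | 90.0% | 90.0% |

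The first row moves from the 50-to-70 category up to 70-to-90. In the second and third rows both values stay in 70-to-90.

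**Where the category changes, with 95% early.** Solving each formula for the later adherence that reaches a cut:

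- Cut at 90: SAP rule (90×44 − 26×95)/18 = 82.8%; dose-weighted (90×722 − 182×95)/540 = 88.3%.
- Cut at 70: SAP rule (70×44 − 26×95)/18 = 33.9%; dose-weighted (70×722 − 182×95)/540 = 61.6%.
- Cut at 50: dose-weighted (50×722 − 182×95)/540 = 34.8%.

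Later adherence of about 83% to 88%, or about 35% to 62%, is therefore placed one category too high. Between about 62% and 83% both rules give the same category.

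**The case against.** The strongest reply is that the definition is explicit, computable and contradicted nowhere, and that nothing important depends on it. Much of this stands. Compliance is a descriptive Safety-set summary. It does not appear in the MMRM or CMH analyses, the imputation model or the subgroup list. The formula is the same in every arm, so comparisons between arms are distorted only if adherence changes differently by arm. The category often stays the same, as two of the examples show. Nor is the dose-weighted value the truth, because it rests on the same self-reported, completed-only questionnaires.

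Three stronger readings are tempting, and the documents do not support them.

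- A reader might infer that compliance will be overstated, because children adhere best at the start. The documents give no adherence data. What follows from the text is that later reports are under-weighted; the sign of any error depends on whether adherence falls or rises.
- A reader might take 59% as a fixed property of the plan. It requires equal completion of weekly and monthly reports. The protocol amendment history notes that activity and compliance data were collected by paper diary for about 6 months before the application was launched, so the early completion rate is an open question.
- A reader might infer that the per-protocol set is affected, since SAP 5.2 lists "Significant deviations in dosing adherence" among possible major deviations. Classification is left to a separate deviation rules document, and nothing says that the 7.3.2 average is the criterion.

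What the reply does not remove is that a rule followed exactly as written gives a mis-weighted figure whenever adherence changes after Month 6. That is more than a preference between equivalent summaries.

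**Conclusion.** The point holds, as a minor one. With equal completion, the first 6 months receive 59%, 46% and 38% of the weight at Months 24, 36 and 48, which is more than twice their share of time at each analysis. At Month 24 the weight runs from about 42% to 74% under the uneven completion patterns assumed above. The bias is zero if adherence is stable, upward if it falls and downward if it rises. In the assumed examples it is 13.5 points in either direction (78.6 − 65.1 and 89.9 − 76.4). The consequence is limited to the compliance summary and its categories. No efficacy result is affected, and an effect on per-protocol membership would need a link that the SAP does not make.

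**What to change.** In SAP 7.3.2, replace the mean of period percentages with one ratio per participant:

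100 × (planned doses − reported missed doses) / planned doses, with both terms summed over all completed reports.

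This is the same as weighting each period by its planned doses. It takes in the three-times-weekly case through the existing denominators of 3 and 13. Apply it also to the summaries by treatment, so that a participant with weekly and monthly reports and one with only monthly reports are measured on the same scale.

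The change corrects for period length, not for missing reports: with all weekly and half of the monthly reports, the first 6 months would still carry 182/(182 + 270) = 40.3% of the weight at Month 24. A summary by phase (Months 1 to 6, 7 to 24, 25 to 36), with the number of completed reports in each, would show this directly.

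The cost is one formula and, if wanted, one table. Every input is already collected or defined.

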6.1.2 DOSING AND ADMINISTRATION

Prior to randomization, the participant or parent/guardian will administer 1 drop of an artificial tear to each eye to demonstrate cooperation and performance with eyedrop instillation. Once study entry procedures have been completed, the investigator's designee will obtain the randomization assignment and drug kit number from the IVRS/IWRS and provide training to the participant or parent/guardian in the correct administration. One drop will be administered to each eye nightly. Detailed instructions are described in the MOP including resupply procedures.

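### For participants moved to three doses a week, the SAP's compliance formula changes only the denominator, so each such reporting period scores 131% to 233% however many planned doses were missed

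*SAP*

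**What the plan says.** SAP 7.3.2 (Treatment Compliance and Modifications) takes the number of missed doses from a weekly, later monthly, questionnaire. For each reporting period, "compliance will be calculated as (Number of Days in the reporting period – Number of Reported Missed Doses During the reporting period"), divided by the "Number of Days in the reporting period × 100 as the expected number of doses is once per day". The period lengths are fixed: "The number of days per dosing period will be 7 for weekly reports, 30 for monthly reports".

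One exception follows: "If the dosing regimen is altered to 3 times/Week dosing for a participant for safety reasons", then "the denominator will only include planned dosing dates (e.g., 3 doses per week period, 13 doses per month period"). The section does not alter the numerator for these participants, does not say how nights without a planned dose are to be counted, and sets no upper limit on the result.

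A participant's compliance is the mean over reporting periods. It is then grouped into classes, the top one being 90% or more with no ceiling, and summarised on the Safety set.

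Elsewhere only one frequency appears. Protocol 6.1.2 states: "One drop will be administered to each eye nightly". Protocol 4.1 and SAP 7.3 likewise describe nightly dosing only.

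**The concern.** The nightly formula works because one dose a day is expected, so days and planned doses are the same number above and below the line. Once the planned number falls to 3 or 13, the two terms must move together. The exception moves only one, so the result is no longer a proportion of planned doses.

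What is at stake is the credibility of the compliance tables. Periods in which a child took none of the planned doses would count as better than fully compliant. Because participant compliance is an unweighted mean over periods, these scores also offset genuinely poor nightly periods. A reader who uses the tables to judge whether the arms received the drug as intended could be misled, to an extent that depends on how many participants were altered.

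**Working it through.** **Inputs, all from SAP 7.3.2.** Days in the period: d = 7 (weekly) or 30 (monthly). Planned doses under the altered regimen: p = 3 or 13. Reported missed doses: m.

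**The plan's own figure.** Three doses a week over 30 days is 30 × 3/7 = 12.86, which rounds to the stated 13.

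**Nightly rule.** Compliance = 100 × (d − m)/d. With m = 0 this gives 7/7 and 30/30 = 100%. With every dose missed it gives 0%. The base formula is sound.

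**Altered rule as written.** Compliance = 100 × (d − m)/p. Taking m to count planned doses only:

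| Report | Planned doses missed | As written | Planned doses in both terms |
|---|---|---|---|
| Weekly | 0 of 3 | 7/3 = 233.3% | 3/3 = 100% |
| Weekly | 2 of 3 | (7 − 2)/3 = 166.7% | (3 − 2)/3 = 33.3% |
| Weekly | 3 of 3 | (7 − 3)/3 = 133.3% | 0% |
| Monthly | 0 of 13 | 30/13 = 230.8% | 13/13 = 100% |
| Monthly | 13 of 13 | (30 − 13)/13 = 130.8% | 0% |

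**Size of the error.** The two rules differ by 100 × (d − p)/p whatever m is: 4/3 = 133.3 percentage points for a weekly report and 17/13 = 130.8 points for a monthly one. The lowest score an altered period can take is 130.8%.

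**Effect on a participant's mean (illustration; the mix of periods is assumed).** Take 24 months of complete reporting: 26 weekly and 18 monthly reports, 44 in all. Suppose 38 periods are nightly at 80% and the last 6 monthly periods are on the altered regimen.

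- Every planned dose missed in those 6: as written (38 × 80 + 6 × 130.8)/44 = 86.9%; matched numerator (38 × 80 + 6 × 0)/44 = 69.1%. The participant moves from the 50-to-under-70 class to the 70-to-under-90 class.
- No planned dose missed in those 6: as written (38 × 80 + 6 × 230.8)/44 = 100.6%; matched numerator (38 × 80 + 6 × 100)/44 = 82.7%. The participant moves from the 70-to-under-90 class to the top class.

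In both cases the shift is 6/44 × 130.8 = 17.8 points.

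**Alternative counting.** If the 4 (or 17) non-dosing nights were also reported as missed, full adherence gives (7 − 4)/3 = 100% and (30 − 17)/13 = 100%, and taking nothing gives (7 − 7)/3 = 0% and (30 − 30)/13 = 0%. The written rule is then exact.

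**The case against.** The strongest reply is the alternative count just shown. The questionnaire's wording is not in the documents, and Protocol 6.1.2 and 6.4 send detail to a Manual of Procedures that is also not available. If families report off-nights as missed, nothing is wrong with the arithmetic. This stands as an assumption that must be declared. It does not rescue the text: a night with no planned dose is not ordinarily a missed dose, and the SAP gives no instruction to count it as one. Without an instruction, two fully adherent children could score 233% and 100% according to how each family read the question.

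It can also be said that the intent is plain, since days stand in for expected doses in both terms, and that values above 200% would be noticed in the listings. That is likely, but the written rule would then have to be corrected at programming.

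On the protocol mismatch, the SAP wording is conditional, and Protocol 7.1 leaves changes in participant management to the investigator. The SAP may only be providing for an event it does not prescribe. That lessens the conflict without removing it.

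Several stronger readings are tempting, and the documents do not support them:

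- **Every altered participant ends in the top class.** This is true of each altered period, not of the mean over all periods, as the 86.9% example shows.
- **The per-protocol set is corrupted.** SAP 5.2 lists "Significant deviations in dosing adherence" as a possible major deviation, but deviations are assigned through a separate rules document with several sources. Nothing says this percentage is the trigger.
- **The output leaves no trace of reduced dosing.** SAP 7.3.1 counts exposure in calendar days and no dedicated summary is planned, but the action taken for adverse events is recorded (Protocol 8.3.4) and deviations and adverse events are listed (SAP 5.2 and 9.1.1).
- **Adherence is inflated more in the 0.03% arm.** The documents give no count of altered participants by arm.

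**Conclusion.** The rule is wrong as written. If missed doses are missed planned doses, every reporting period on the altered regimen scores between 130.8% and 233.3%. It overstates adherence to planned doses by 130.8 points (monthly) or 133.3 points (weekly), whatever the child actually took. The participant's mean rises by that amount times the share of altered periods, and the arm-level descriptive summaries rise with it.

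The consequence is limited. The number of participants affected is not stated and could be zero. Compliance is descriptive and enters no efficacy model, so the analyses on the full analysis set are untouched. The per-protocol sensitivity analyses could be affected only if this value is used to screen for dosing-adherence deviations, which the documents do not say.

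Separately, the SAP's reference to a three-times-a-week regimen does not match the nightly-only dosing in Protocol 4.1 and 6.1.2 and SAP 7.3. The passages must be reconciled; no view is taken here on which is right.

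**What to change.** In SAP 7.3.2, define compliance for each reporting period as 100 × (planned doses − missed planned doses)/planned doses. Use the SAP's own planned numbers in both places: 7 or 30 for nightly periods, and 3 or 13 for periods on the altered regimen. Add one sentence stating that nights without a planned dose are not counted as missed, and check that the questionnaire responses can be read that way.

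Reconcile the three-times-a-week reference with the nightly dosing text in the protocol and in SAP 7.3.

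The cost is one corrected formula, one added sentence and a few lines of programming, plus a clarification between the two documents. No new data are required if the questionnaire responses already count only planned doses as missed.
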